### **Inclusion criteria for real-time data capture**

In addition to meeting the standard inclusion criteria outlined in section 3.2.1.1, those participants invited to take part in the real-time data capture will also be required to meet the following criteria:

- 1. Participant owns/or has access to either a smartphone (iOS or android) or tablet which has video, audio/microphone and photographic capabilities and access to either the Apple app store or google play store to download the app;
- 2. Participant is willing and able to take part in the real-time data application task and respond to a series of questions/tasks fielded to them via the application over the course of 10 days;

AND

Is willing to respond to some brief questions following the real-time data capture task about their experience of using the app and completing the tasks, either during their interview or in a 5-10 minute telephone call following completion of the task

- 3. Participant would feel comfortable recording short videos of themselves and providing audio commentary in response to questions/tasks.

### **3.2.1.2 Exclusion Criteria**

Any participant presenting with any of the following will not be included in the study.

- 1. Participant has received oral or injectable systemic corticosteroids in the last 4 weeks (28 days) for the management of their nasal polyps
- 2. Participant has a diagnosis of cystic fibrosis;

3. Participant has a diagnosis of eosinophilic granulomatosis with polyangiitis (also known as Churg Strauss syndrome), Young's, Kartagener's or dyskinetic ciliary syndromes);
4. Participant has a diagnosis of antrochoanal polyps;
5. Participant has a diagnosis of nasal septal deviation occluding one nostril;
6. Participant has had acute sinusitis or upper respiratory tract infection in the last two week;
7. Participant has ongoing rhinitis medicamentosa (rebound or chemical induced rhinitis);
8. Participant has had an asthma exacerbation requiring admission to hospital in the last four weeks;
9. Participant is currently or has previously taken part in a clinical trial for nasal polyps;
10. Participant is unwilling or unable to comply with the requirements of the study or has a physical or mental condition or learning difficulties that, in the opinion of the physician, may affect the participant's ability to participate in the study, the responses he/she might provide or their ability to provide consent.

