## 1 INTRODUCTION/BACKGROUND

Nasal polyps is considered to be a subgroup of chronic rhinosinusitis and is defined as a chronic inflammatory disease of the nose and sinuses. Nasal polyps is characterized by the presence of two or more of the following symptoms: watery rhinorrhea from the nose (anterior), postnasal drainage (posterior), nasal obstruction and a temporary or in extreme cases permanent decreased sense of smell (anosmia). The standard of care for patients with severe nasal polyps includes intranasal steroids, oral corticosteroids and surgery. However, there are currently no established criteria for surgery; candidacy for surgery is considered on the basis of level of nasal obstruction, symptom severity, impacts to the patient and the perceived risks/benefits of surgery.

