Participants will be recruited through a combination of primary care physicians/general practitioners and ear, nose and throat (ENT) specialists. Physicians will identify suitable participants for the study using the case report form (CRF) (Appendix 4). Participants identified by their physician will be provided with two copies of the information and consent form (ICF) to read and sign to indicate informed consent/assent if they wish to participate in the study (Appendix 5) – one for the participant to keep and one that the recruitment agency will send to AV. Participants will be given the opportunity to consider the information provided in the ICF and to ask the recruitment agencies/recruiting physician or AV any questions about the ICF before providing their informed consent. If the participant verbally agrees to take part and also signs the ICF, they will be informed that their name and contact information will be passed to the respective recruitment agencies in each country who will contact them to screen them into the study and collect demographic information about each participant (Appendix 6), ensuring study quotas are met for obtaining a representative sample as outlined in section 3.2.2. No information will be passed to the recruitment agencies until verbal and informed consent has been obtained from the participant. After informed consent has been obtained, the participant's physician will release the CRF data to the respective recruitment agencies in each country (Appendix 4); confirming that the participant meets the study inclusion requirements, and providing additional information about the participant's clinical condition and medical history. MedQuest Global will be responsible for ensuring that

any US participant who opts in to take part in the real-time data capture activities meets the criteria as outlined in section 0.

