If the participant meets the criteria for inclusion in the study section 3.2.1.1 the recruiter will organize enrolment into the app task (where applicable) and schedule a time for the participant to attend the 120-minute interview visit. Of the 10 US participants who elect to take part in the app task five will complete the app task prior to their scheduled interview, and the remaining five will complete the app task after their interview. For the five US participants who complete the app task prior to their interview they will be asked about their experience of completing the app task at the end of the interview. For the five US participants who complete the app task after their interview, a separate a brief telephone call (approximately 5-10 minutes) will be scheduled with the participant to ask them brief questions about their experience. The questions relating to the participant experience of completing the app task are provided in Appendix 7.

In terms of compensating participants for their involvement in the study the following compensation structure will be employed:

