### The role of the interviewer before the interview:

1. Check that the patient's clinician has completed the CRF and screener and that the patient meets the inclusion and exclusion criteria.
2. Check the patient has provided written informed consent and provided verbal consent for the interview to be audio-recorded.

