**[TO INTERVIEWER]**

## Interviewer instructions

- You may need to keep reminding the participant to read and think aloud. Please have the patient read aloud the response they have chosen so this can be recorded.
- If the participant has difficulty reading a particular item, offer to read it for them and make a note of this.
- **Make sure you are non-judgmental in your tone** when probing. If the participant hesitates when answering, use one or more of the following probes, or similar questions to elicit comments from them. Please feel free to vary which ones you ask for each questionnaire item – rather than going through each one in rote fashion and getting one word answers. **Not every probe has to be used for every item/participant.**
- **Asking why:** if appropriate, probe further by asking the participant why they have answered the interview question in that way.
- If the patient has chosen to **skip a question** remember to ask why they have chosen to do so.
- If the patient has chosen “0” or “not applicable” option for any question ask why they have made this selection
  - Was the question not relevant? (e.g. they do not experience this symptom)
  - Is the question relevant, although they might not be currently experiencing this symptom?
- Wherever possible, please make brief notes in the empty boxes provided for each item to summarize:
  - How the question was **understood** by the participant?
  - Was the concept **relevant** to the participant?
  - How **easy/difficult** was it for the participant to choose their answer?
  - Why did they choose the answer they did? [please record their answers in the box below]

Date:  /  / 2017  
MM DD

Center Number: /\_\_\_/\_\_\_/

Participant N°: /\_\_\_/\_\_\_/

• **Cognitive debriefing of the SNOT-22**

ADELPHI VALUES

Understanding	Relevance	Recall period	Response Options

[INSTRUCTION 1] Below you will find a list of symptoms and social/emotional consequences of your rhinosinusitis. We would like to know more about these problems and would appreciate your answering the following questions to the best of your ability. There are no right or wrong answers and only you can provide us with this information. Please rate your problems as they have been over the past two weeks. Thank you for your participation. Please do not hesitate to ask for assistance if necessary.
			

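### The infection, systemic-steroid and asthma-admission windows have no reference date and are not described as re-asked when SNOT-22, VAS and app data are collected, so an intercurrent event could distort those summaries unidentified

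*Combined protocol and SAP*

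**What the plan says.** **The windows.** Section 3.2.1.2 lists three dated exclusions: item 1, "Participant has received oral or injectable systemic corticosteroids in the last 4 weeks (28 days) for the management of their nasal polyps"; item 6, "Participant has had acute sinusitis or upper respiratory tract infection in the last two week"; and item 8, "Participant has had an asthma exacerbation requiring admission to hospital in the last four weeks". None says which date the window is counted back from.

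**Who checks, and when.** Section 3.2 states: "Physicians will identify suitable participants for the study using the case report form (CRF) (Appendix 4"). The agency then screens against the quotas, arranges the app task where it applies, and schedules the interview. No maximum time from CRF to interview or app is given. Of the ten US app participants, "five will complete the app task prior to their scheduled interview"; the other five do it afterwards.

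**Before the interview.** Appendix 7 tells the interviewer to check that the "clinician has completed the CRF and screener and that the patient meets the inclusion and exclusion criteria". The scripted introduction covers purpose, confidentiality, recording and consent. It contains no question about events since the CRF. The app entry criteria (section 3.2.1 and Appendix 6) contain no infection or steroid item.

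**What the data refer to.** The SNOT-22 instruction reads "Please rate your problems as they have been over the past" two weeks. Each VAS in Appendix 8 asks about the previous 24 hours. The app runs for ten days (section 3.3).

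**How the data are used.** Section 4 summarises SNOT-22 and VAS totals, items and response distributions, and describes numerical app items by means and ranges. Section 2.2 makes day-to-day variability an aim of the app task, and Appendix 9 proposes daily ratings in order to report it.

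**The concern.** By excluding patients with a recent respiratory infection or systemic steroid course, the protocol itself treats those states as unsuitable for describing the nasal polyp experience. The windows apply to the time before the CRF, while the ratings describe the time before the interview or during the app task. Nothing ties the two together.

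An intercurrent cold produces sneezing, runny nose, cough, facial pressure and loss of smell, all of which SNOT-22 or the VAS ask about. It would raise scores and add day-to-day swings. A steroid course or polypectomy after the CRF would be expected to lower them in someone enrolled as severe. Such events are plausible here: participants must be current candidates for polypectomy, and section 1 says "The standard of care for patients with severe nasal polyps includes intranasal steroids, oral corticosteroids and surgery".

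What is at stake is the interpretation of the score summaries in section 4 and of the variability described from the app. No step requires these events to be recorded, so affected participants could not be reliably picked out afterwards.

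**Working it through.** The plan states no figure on this point, so there is none to reproduce. The check is arithmetic on dates, followed by an illustration under an assumed infection rate.

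**Inputs from the documents**
- Infection window 14 days, steroid window 28 days (section 3.2.1.2)
- SNOT-22 recall 14 days (Appendix 7), VAS recall 24 hours (Appendix 8)
- App period 10 days, 10 participants (section 3.3); 30 interviews (section 3.4)

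**Inputs not in the documents**
- Gap *g* in days from CRF to interview: unknown
- Infection rate *r*: assumed 1 to 4 per person-year

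**Step 1: days the CRF check cannot cover.** The unchecked part of the SNOT-22 recall is min(*g*, 14) of 14 days. The unchecked part of the 28 days before the interview, for steroids, is min(*g*, 28).

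| Gap *g* (days) | SNOT-22 recall unchecked | Steroid look-back unchecked |
|---|---|---|
| 0 | 0 of 14 | 0 of 28 |
| 7 | 7 of 14 | 7 of 28 |
| 14 | 14 of 14 | 14 of 28 |
| 28 or more | 14 of 14 | 28 of 28 |

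The 24-hour VAS recall is wholly unchecked once *g* is 1 or more. For the five participants who finish the ten app days before the interview, *g* is at least 10, so at most 14 − 10 = 4 of the 14 SNOT-22 days are covered.

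**Step 2: illustration for infection.** The chance of at least one onset in *d* unchecked days is p = 1 − exp(−*r* × *d*/365).

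| Setting | *r* = 1 | *r* = 4 |
|---|---|---|
| *d* = 14 (every gap at least 14) | p = 3.8%; 30p = 1.1 | p = 14.2%; 30p = 4.3 |
| *d* = 7 (every gap 7) | p = 1.9%; 30p = 0.6 | p = 7.4%; 30p = 2.2 |
| *d* = 10 (app period) | p = 2.7%; 10p = 0.3 | p = 10.4%; 10p = 1.0 |

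The first row is an upper scenario, because it sets all 30 gaps at 14 days or more. No rate for steroid courses or surgery can be taken from the documents, so none is computed.

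**Step 3: leverage.** One affected participant moves a mean over 30 by 1/30 of that person's own shift, and a mean over 10 by 1/10 of it. The same person can set the reported minimum or maximum outright.

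**Step 4: the steroid item on the form.** Section 3.2.1.2 makes recent systemic steroid use an exclusion. The CRF in Appendix 4 lists the same statement as inclusion item 1, under a rule that any NO among those items bars the patient. The two places contradict each other, so the tick box does not apply the window as section 3.2.1.2 states it.

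**The case against.** **There is a check before the interview.** Appendix 7 does tell the interviewer to confirm that the patient meets the criteria. A reader might infer that eligibility is looked at only once, by the physician; the documents do not support that. The step reads as a review of completed forms, however, and no question about the period since the CRF is scripted. What stands is narrower: re-asking the windows is not described.

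**The relevance judgement is largely protected.** Every SNOT-22 and VAS item carries a probe on whether the problem belongs to the participant's nasal polyps. Participants are also asked to explain their answers, and a zero must be followed up, including whether the item is relevant though not currently experienced. Concept elicitation is not tied to a fortnight. A reader might infer that a cold or steroid course would bias the content-validity conclusion. These probes make that unlikely, provided the participant can tell a cold from polyps. They do not alter the score that goes into the summaries.

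**Infection is partly under study.** The Appendix 7 symptom list includes sinus infections and general illness and infection. Discarding or postponing affected participants could lose experience the protocol wants to hear about. This stands, and it argues for recording and flagging over compulsory rescheduling.

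**The consequences are modest.** Section 3.3.1 declares no endpoints and says the questionnaires are completed for debriefing. The daily app ratings are examples, and one example task asks about treatments used that day. This stands too, but section 4 still reports the scores, and no example task asks about infection.

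**Surgery has no window.** Items 1, 6 and 8 concern steroids, infection and asthma admission. A reader might infer that intervening surgery breaches a dated exclusion; none exists. The only link is the requirement to be a current polypectomy candidate, so surgery can be recorded and flagged but there is no window to re-meet.

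**Conclusion.** The point holds as a gap in timing and recording. The windows have no reference date, no maximum interval is set, and no passage says they are re-asked at the interview or for the app period. Followed exactly, the plan could leave an intercurrent infection, steroid course or polypectomy inside the SNOT-22/VAS summaries and the app variability with no reliable way to identify it.

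The size is uncertain. A reader might take 1.1 to 4.3 of 30 as an estimate. It is not: it requires every gap to be at least 14 days and rests on an assumed 1 to 4 infections per person-year, neither of which comes from the documents. Shorter gaps reduce it, and it falls to zero if CRF and interview share a date. The app-period figure of about 0.3 to 1.0 of 10 uses the same assumed rate.

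The exposure is confined to descriptive results. It does not undermine the concept elicitation or the main content-validity conclusions. It is worth acting on because the remedy is cheap and the information cannot be reliably recovered later. The contradiction over the steroid item stands independently of any assumption.

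**What to change.** 1. In section 3.2.1.2, state the date from which each window is counted.
2. Add one scripted question to the Appendix 7 introduction, and at app start and end: since the CRF, has the participant had a cold or sinus infection, systemic corticosteroids, a hospital admission for asthma, or polyp surgery? Record the answer and the approximate date.
3. Record the CRF-to-interview gap in days. The CRF already carries its completion date.
4. In section 4, keep all concept elicitation data, flag affected participants, and present the SNOT-22/VAS summaries and the app variability with and without them. Rescheduling need not be mandatory.
5. Reconcile the systemic corticosteroid item between section 3.2.1.2 and the CRF in Appendix 4, including the rule attached to the CRF inclusion items.

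The cost is about one minute per contact, a few lines of text and a small extra table. It needs no additional participants or procedures and changes no treatment. With 10 app participants the with-and-without comparison will be coarse, and it should be read as a description only.

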### **3.2.2 Sampling**

Twenty adult participants in the US, and 10 participants in Germany with severe, recurrent nasal polyps who have received nasal polyp surgery in the past 10 years prior to screening will take part in this study. Of these 30 participants, 10 of the 20 US participants (50%) will also complete the real-time data capture app task. The real-time data capture app task will not be conducted in Germany.

In addition to meeting the inclusion/exclusion criteria outlined in section 3.2.1, AV will employ a purposive approach to sampling to ensure patients with a range of demographic, educational and clinical characteristics are recruited. To achieve representation of demographics and clinical characteristics within the sample, sampling quotas will be employed. Overall sampling quotas for the US are detailed in Table 1 and for Germany outlined in Table 2. German demographic data is not collected in regards to ethnicity and race separately, and thus, the quotas have been adjusted to fit the norm in Germany. Quotas may be relaxed if recruitment proves challenging. The clinical and demographic information to support the achievement of these quotas will be captured using the clinician-completed case report form (CRF) and patient-completed demographic form.

**Table 1: Quotas for US participants (n=20)**

Participant characteristics		Adults		Total
		18-45	46+	
Age		≥6	≥6	≥12
Gender	Male	≥2	≥2	≥6
	Female	≥2	≥2	≥6
Ethnicity	Hispanic or Latino (of any race)			≥6
	Non-Hispanic or Latino			≥6
Race	White			≥4
	Black/African American			≥4
	Multi-racial			≥2
	Other race/ethnicities 
 
• Asian or Pacific Islander
 
• Native American or Alaska native
 
• North African or Middle Eastern
 
• Other (specified by participant)
 
			≥2
Education	Some high school			≥3
	College or higher			≥3
Polypectomy surgery	In past 2 years			≥6
	In past 3-10			≥6

**Table 2: Quotas for German participants (n=10)\***

Participant characteristics		Adults		Total
		18-45	46+	
Age		≥3	≥3	≥6
Gender	Male	≥2	≥2	≥4
	Female	≥2	≥2	≥4
Race	White Caucasian			≥4
	Non-Caucasian			≥2
Education	Some high school (German equivalent)			≥3
	College or higher (German equivalent)			≥3
Polypectomy surgery	In past 2 years			≥3
	In past 3-10			≥3

\*Note that German quotas have no ethnicity category as this is not typically collected in German. The race category is also simplified in line with what is typically expected in Germany.

### **3.3 Data Source / Data Collection**

All recruited participants will take part in a 120-minute telephone interview. A semi-structured interview guide will be used to guide the conduct of the CE interview section and CD interview section and will ensure that all topics of interest are discussed (Appendix 7). The interview guide is designed to be used as a guide, not as a script to be read verbatim. The interviewer will therefore be flexible in the order of questioning, following the lead of the participant and asking appropriate questions when topics of interest arise. All interviews will be audio recorded and transcribed verbatim for the purpose of analysis. Any identifiable information (e.g. participant or doctor's names) will be removed from the transcripts such that they are fully anonymized.

#### **Concept elicitation (55 minutes)**

During the CE section of the interview participants will be asked a series of broad open-ended questions designed to encourage them to talk openly and as spontaneously as possible about their experience of having nasal polyps and how it affects their life. In addition to speaking open-endedly about their experiences, participants will be asked more focused questions designed to probe on issues that they may not have mentioned during the course of the interview or concepts/statements that require additional clarification. Asking probe questions in a dynamic and 'as required' fashion information will be important for ensuring all study objectives are met and all study questions and topics of interest are explored, thus supporting the identification of the concepts that are most important to patients and the terminology they use to describe their experiences.

#### **Cognitive debriefing (60 minutes)**

During the CD section of the interview participants will be asked to complete the PRO instruments using a 'think aloud' process in which they will be asked to speak aloud their thoughts as they read the instructions, item and complete the questions. After completion of each 'think aloud' exercise, participants will take part in in-depth CD centered on their experience of completing the instruments, with particular focus on the relevance and understanding of the items, instructions, response options and recall period. In addition, the participants will be encouraged to discuss what level of change in their symptoms would they consider meaningful and important and how this would relate to changes on the items scores.

The questionnaires (Appendix 8) that will be used in the cognitive debriefing task will be sent to participants in the mail in advance of their interview by the recruitment agency. Participants will not be required to complete these until instructed to during the interview. Following the interview, participants will be asked to send the questionnaires

back to the recruitment agency using a stamped addressed envelope which will be supplied to them.

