The patient experience of nasal polyps is typically assessed via clinical interview and review of clinical history and the use of existing patient-reported outcome instruments (PROs). PRO instruments used with patients with nasal polyps typically include single item visual analogue scales (VAS), whereby patients are asked to evaluate overall symptom severity, or the severity of individual symptoms of nasal polyps along a continuum, typically of 10cm or 100 mm whereby 0 represents 'no symptom' and '10 or 100 represents 'as bad as you can imagine', Scores of 0-3 (or 0-30) are defined as mild disease, >3-7 (or >30-70) as moderate disease and >7-10 (or >70-100) as severe disease. Historically, these items have not been developed based on patient characterization and therefore there is a need to understand the appropriateness of these measures for use within this population. The Sino-Nasal Outcomes Test (SNOT-22) is also used frequently within clinical research and as a clinical trial endpoint to measure health-related quality of life associated with rhinosinusitis with or without nasal polyps. The SNOT-22, a derivative of the SNOT-20, is a modification of the 31-Item Rhinosinusitis Outcome Measure (RSOM), containing 22 nose, sinus, and general health-related quality of life (HRQoL) items. Within the SNOT-22 patients are required to indicate the level of to which each listed nasal, sinus or HRQoL experience has been affected on a 6-point scale ranging from 0 (No problem) to 5 (Problem as bad as it can be) and also identify the five most important items affecting their health. Existing evidence supports the psychometric validity of the SNOT-22 among patients with rhinosinusitis; with evidence of high reliability and sensitivity to clinical change. Preliminary searches, however, suggest that evidence regarding the content validity of the SNOT-22 may be lacking.

GlaxoSmithKline (GSK) is embarking on a clinical program to assess treatment of severe, recurrent nasal polyps with an anti-interleukin-5 (anti-IL5) (mepolizumab). Patient symptomatic endpoints will form the basis for the assessment of treatment benefit of nasal polyp therapies. Currently, there is a lack of published qualitative data regarding nasal polyps to understand the symptoms (specific symptoms, duration,

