### SYMPTOM LIST

Symptom	Tick if mentioned spontaneously (✓)
Congestion	
Runny nose	
Nasal swelling	
Loss of smell	
Change in smell	
Nose bleed	
Post-nasal drip/throat mucus	
Nasal pain	
Nasal pressure	
Sneezing	
Visible polyps	

Symptom	Tick if mentioned spontaneously (✓)
Mucus/catarrh	
Nasal tightness	
Sinus blockage	
Sinus inflammation	
Sinus infections	
Difficult breathing	
Wheezing	
Cough	
Head/facial pressure	
Headache	
Dizziness	
Dry throat/mouth	
Loss of taste	
Distorted voice	
Ear congestion	
Illness and infection	
Patient mentioned symptoms not currently in list:	

**[Note to interviewer]:** Now ask the participant the following questions about each sign/symptom that they mentioned spontaneously. Allow the participant to answer spontaneously at first and only probe further if the participant is having difficulty discussing his/her experience or hasn't previously mentioned the probed topics. Please note that the probes are to be used as a guide and they may not all need to be asked.

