**Appendix 8: Questionnaires for use in cognitive debriefing interview****QUESTIONNAIRES**

This document contains a number of questionnaires for you to complete, during your telephone interview with Adelphi Values about your nasal polyps. Within this document you will see a series of images of the questionnaire in electronic format, designed for use on a smartphone. Although you will see the questionnaire in this format you will be required to provide your answers on paper in this document by checking the relevant answer.

**IMPORTANT:** This document is for use **DURING** your telephone interview **ONLY**. Please do not complete any of the questionnaires inside this document until you are told to do so during your telephone interview.

[figure not shown]

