**Please keep this document and the pre-paid mail return envelope safe until your telephone interview.**

**Following the telephone interview, please mail this document to MedQuest (recruitment agency), using the pre-address and pre-paid mail envelope that has been provided.**

## Questionnaire 1: SNOT 22

---

[figure not shown]
CCI - This section contained Clinical Outcome Assessment data collection questionnaires or indices, which are protected by third party copyright laws and therefore have been excluded.

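### The SNOT-22 and VAS booklet reaches participants before the interview with no stated bar on opening or reading it, which puts spontaneous elicitation and a first-reading think-aloud at risk

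*Combined protocol and SAP*

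**What the plan says.** Section 3.1 places concept elicitation before cognitive debriefing, and the Appendix 7 timetable does the same (5 minutes of introduction, 55 of elicitation, 60 of debriefing). In the elicitation part, section 3.3 wants participants to "talk openly and as spontaneously as possible about their experience of having nasal polyps". The Appendix 7 symptom list gives the interviewer a column headed "Tick if mentioned spontaneously". Section 2.2 counts the language patients use among the things to be identified.

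The interviews are by telephone, so the Appendix 8 questionnaires "will be sent to participants in the mail in advance of their interview by the recruitment agency" (section 3.3, Cognitive debriefing). The booklet holds the SNOT-22, described in section 1 as "containing 22 nose, sinus, and general health-related quality of life (HRQoL) items", and six VAS labelled A to F.

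The safeguards in the available text are these:

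- Section 3.3: "Participants will not be required to complete these until instructed to during the interview".
- Appendix 8, front page, which restricts the document to use during the call: "telephone interview ONLY. Please do not complete any of the questionnaires inside this document until you are told to do so".
- Appendix 8, next page: "Please keep this document and the pre-paid mail return envelope safe until your telephone interview".

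**The concern.** Putting elicitation first works only if participants have not already studied the items. A booklet at home before a two-hour call invites a look, and nothing in the available text asks participants not to look.

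Three things depend on this:

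- **Patients' own language.** Appendix 7 opens elicitation by asking what the participant calls the condition, and then uses that term. The SNOT-22 instruction supplies the word rhinosinusitis, and debriefing later asks what that word means to the participant. Someone who read ahead has met it before either question.
- **The comparison of concepts with items.** Section 2.2 uses the concepts from elicitation to check whether the instruments cover them. If some volunteered terms came from the instruments, the two sides are no longer fully independent. Any bias would tend to favour the instruments. Section 4 also judges saturation partly by whether new terms still appear, and vocabulary taken from a shared booklet could affect that.
- **The think-aloud.** It is meant to capture thoughts as the items are read. On a second reading, some hesitation or misreading may already have been resolved.

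**Working it through.** There is no statistical figure to reproduce: the study has no hypotheses, endpoints or power calculation. The check is a reading of the text plus one count.

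**Step 1: does any available text restrict opening or reading?**

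- Section 3.3 restricts completing.
- The Appendix 8 front page restricts use to the interview, and restricts completing.
- The Appendix 8 next page asks for safe keeping.
- Packaging is not described anywhere.
- In Appendix 7, none of the interviewer's pre-interview checks, the scripted introduction or the opening of the debriefing section asks whether the booklet was opened or read.
- Section 5 (Limitations) does not mention it.
- The consent form (Appendix 5) and the text of section 7.1 on the recruitment agencies were not available, so an instruction there cannot be excluded.

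**Step 2: how many participants receive the booklet?** All interviewees: 20 (US) + 10 (Germany) = 30.

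**Step 3: how far does the booklet overlap the spontaneous-mention list?** The booklet holds 22 + 6 = 28 ratings. The SNOT-22 form is redacted in Appendix 8, so its item names come from the debriefing tables in Appendix 7. The list has 11 + 16 = 27 symptoms over its two table parts. The count uses the English wording.

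Nearly word for word:

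1. Runny nose (SNOT-22 item 4)
2. Loss of smell (VAS D; item 12)
3. Post-nasal drip/throat mucus (item 6; VAS C)
4. Sneezing (item 3)
5. Cough (item 5)
6. Head/facial pressure (item 11; VAS E)
7. Dizziness (item 9)
8. Loss of taste (item 12)

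8 / 27 = 0.296, or 30%.

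Adding close synonyms, by judgement:

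9. Congestion (item 2, nasal blockage; VAS A, nasal obstruction)
10. Mucus/catarrh (item 7 and VAS B, discharge; VAS C)
11. Ear congestion (item 8, ear fullness)

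11 / 27 = 0.407, or 41%.

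**Step 4: what does the overlap show?** It shows where borrowed wording could not be told apart from the participant's own. It does not measure contamination, because most of these are everyday words that patients could volunteer unprompted. The documents give no rate of reading ahead and no effect of reading on what is said.

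**Step 5: which parts of the interview are protected?** Appendix 7 has the interviewer probe every listed symptom that was not volunteered. Open questions then look for anything left out: question 9 (other symptoms), question 26 (anything else) and question 29 (missing from the SNOT-22). These protect coverage. They cannot recover whether a term was the participant's own, nor correct a tick for spontaneous mention.

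**The case against.** A telephone interview with a paper think-aloud needs the forms in the participant's hands, so mailing them ahead is reasonable. That stands, and the fix keeps the mailing.

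The front page of Appendix 8 does more than forbid early completion: it confines the document to the interview. Many participants may take that as a reason not to browse. This is a real partial safeguard, although it does not mention reading.

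The instruments' relevance and clarity do not rest on spontaneous mention. Relevance is asked item by item in debriefing, and most terms are probed for meaning. Reading the booklet cues listed concepts; it does not obviously hide unlisted ones. Sleep, emotional and work impacts are named by the guide's own questions 17, 18 and 20, so reading the matching SNOT-22 items spoils little there. All of this stands and narrows the point to the spontaneous/probed distinction, patients' own language and the first reading.

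Three stronger readings are tempting, and the documents do not support them:

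- A reader might infer that the booklet goes out unsealed. The text is silent on packaging.
- A reader might infer a number of primed interviews from an assumed read-ahead rate. The documents give no rate, and having read the items is not the same as being influenced by them.
- A reader might infer that a planned agreement statistic is inflated. There is none: section 4 rules out quantitative analysis of how often issues are mentioned.

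**Conclusion.** The concern holds as a design risk, not as a demonstrated bias. The booklet arrives before elicitation. The stated safeguards cover use, completion and safe keeping. No available text covers sealing, opening, reading, or asking about it afterwards.

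Up to 30 interviews are open to the risk, and the number affected cannot be computed. The overlap of 8 of 27 listed symptoms (30%), or 11 of 27 (41%) with judged synonyms, indicates how much of the spontaneous-mention record could be ambiguous if a participant had read ahead. The effect on coverage of concepts should be limited. The effect on the spontaneous/probed distinction, on patients' own terms and on the think-aloud has no safeguard beyond the restrictions already stated.

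This rests on two assumptions: that the consent form and section 7.1 add no instruction on reading, and that some recipients would look if not told otherwise. The change is worth making because it costs so little.

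**What to change.** - **Mailing (section 3.3).** Put the questionnaires in a sealed inner envelope, to be opened on the interviewer's cue at the start of cognitive debriefing.
- **Appendix 8.** Widen the instruction to do not open, read or complete, and print it on the outside of the envelope, since the current notice is on the booklet itself.
- **Appendix 7.** At the start of debriefing, add the cue to open the envelope and one question recording whether the booklet was opened or read earlier. Asking it after elicitation avoids drawing attention to the items beforehand.
- **Section 4 and the report.** Note prior reading descriptively when presenting spontaneous mentions and patient language. Do not add a quantitative subgroup comparison, which section 4 rightly excludes at this sample size.

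**Cost.** About 30 envelopes, short wording changes and under a minute per interview.

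**What it does not solve.** Some participants may still open the envelope, and only those who say so will be identified. Exposure to the nasal obstruction and overall VAS at screening (Appendices 1, 2 and 4) remains. The five US participants who do the app task before the interview may also meet the overall VAS there, since Appendix 9 lists it as one possible response format. The report should state this remaining exposure.
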